7.3 Reporting to Eli Lilly

Eli Lilly must be notified within 24 hours of investigator and/or institution receiving notification of any “serious” and/or “unexpected” adverse event experienced by a patient participating in the Study and receiving Study Drug that is possibly related, based on Investigator’s assessment, to the Study Drug. For purposes of this requirement, “serious” means: (1) death; (2) in-patient hospitalization or prolonged hospitalization; (3) life-threatening; (4) persistent or significant disability or incapacity; (5) congenital anomaly or birth defect; or (6) other serious events that may jeopardize the patient and may require medical or surgical intervention to prevent one of the other five listed outcomes. Serious adverse events should be reported to Lilly using a CIOMS Form or other form acceptable to Lilly. Investigator and Institution further agree to make available promptly to Lilly such records as may be necessary and pertinent for Lilly to further investigate an adverse event in the Study that is possibly associated with the Study Drug.

All instances of reversible posterior leukoencephalopathy must be reported to Eli Lilly via the SAE mechanism.

Any venous or arterial event leading to discontinuation of ramucirumab therapy will be considered serious and should be reported to Eli Lilly via the SAE mechanism

7.4 Exceptions to Expedited Reporting

Events that do not require expedited reporting as described in Section 7.1 include:

- planned hospitalizations
- hospitalizations < 24 hours
- respite care
- events related to disease progression

Events that do not require expedited reporting must still be captured in the EDC.

8.0 PHARMACEUTICAL INFORMATION

8.1 Ramucirumab (Cyramza)

8.1.1 Ramucirumab Description

Ramucirumab is a recombinant human IgG1 monoclonal antibody that specifically binds to vascular endothelial growth factor receptor 2. Ramucirumab has an approximate molecular weight of 147 kDa. Ramucirumab is produced in genetically engineered mammalian NS0 cells.

8.1.2 Clinical Pharmacology

Ramucirumab is a vascular endothelial growth factor receptor 2 antagonist that specifically binds VEGF Receptor 2 and blocks binding of VEGFR ligands, VEGF-

A, VEGF-C, and VEGF-D. As a result, ramucirumab inhibits ligand-stimulated activation of VEGF Receptor 2, thereby inhibiting ligand-induced proliferation, and migration of human endothelial cells. Ramucirumab inhibited angiogenesis in an in vivo animal model.

8.1.3 Pharmacokinetics and Drug Metabolism

The pharmacokinetic (PK) characteristics of ramucirumab are similar for patients with gastric cancer, NSCLC, and mCRC based on a population PK analysis. The mean (% coefficient of variation [CV%]) clearance for ramucirumab was 0.015 L/hour (30%) and the mean terminal half-life was 14 days (20%).

8.1.4 Supplier

Ramucirumab is an investigational agent for this trial and will be supplied by Lilly Oncology, free of charge to the patient.

8.1.5 Dosage Form and Preparation

Ramucirumab is available in two dose strengths:

- 100 mg/10 mL (10 mg per mL) solution, single dose vial
- 500 mg/50 mL (10 mg per mL) solution, single dose vial

8.1.6 Storage and Stability

Store vials in a refrigerator at 2°C to 8°C (36°F to 46°F) until time of use. Keep the vial in the outer carton in order to protect from light.

8.1.7 Administration

Calculate the dose and the required volume of ramucirumab needed to prepare the infusion solution. Vials contain either 100 mg/10 mL or 500 mg/50 mL at a concentration of 10 mg/mL solution of ramucirumab.

Withdraw the required volume of ramucirumab and further dilute with only 0.9% Sodium Chloride Injection in an intravenous infusion container to a final volume of 250 mL. Do not use dextrose containing solutions.

Gently invert the container to ensure adequate mixing.

DO NOT FREEZE OR SHAKE the infusion solution. **DO NOT** dilute with other solutions or co-infuse with other electrolytes or medications.

Store diluted infusion for no more than 24 hours at 2°C to 8°C (36°F to 46°F) or 4 hours at room temperature (below 25°C [77°F]).

Discard vial with any unused portion of ramucirumab.

Visually inspect the diluted solution for particulate matter and discoloration prior to administration. If particulate matter or discolorations are identified, discard the solution.

Administer diluted ramucirumab infusion via infusion pump over 60 minutes through a separate infusion line. Use of a protein sparing 0.22 micron filter is recommended. Flush the line with sterile sodium chloride (0.9%) solution for injection at the end of the infusion.

8.2 Atezolizumab (Tecentriq)

8.2.1 Description

Atezolizumab is a human monoclonal antibody based on a human IgG1 framework containing heavy chain VHIII and light chain VκI subgroup sequences. The recombinant antibody consists of two heavy chains (448 amino acid residues each) and two light chains (214 amino acid residues each) with inter- and intra-chain disulfide bonds that are typical of IgG1 antibodies. Atezolizumab incorporates an amino acid substitution (asparagine to alanine) at position 298 in the CH2 domain of each heavy chain resulting in a non-glycosylated antibody that has minimal binding to Fcγ receptors and, consequently, prevents Fc-effector function and depletion of cells expressing PD-L1 at expected concentrations in humans. Therefore, atezolizumab lacks the N-linked oligosaccharides typically observed on other CHO-derived monoclonal antibodies.

8.2.2 Pharmacokinetics and Drug Metabolism

On the basis of available preliminary PK data (0.03–20 mg/kg), atezolizumab appeared to show linear pharmacokinetics at doses ≥ 1 mg/kg. For the 1-mg/kg and 20-mg/kg dose groups, the mean apparent CL and the mean Vss had a range of 3.20 to 4.44 mL/day/kg and 48.1 to 65.7 mL/kg, respectively, which is consistent with the expected profile of an IgG1 antibody in humans.

8.2.3 Supplier(s)

Atezolizumab will be commercially available.

8.2.4 Dosage Form and Preparation

The atezolizumab drug product is provided in the following configurations:

- (1) The atezolizumab drug product produced using the Phase I manufacturing process is provided in a single-use, 2-cc USP/Ph. Eur. Type 1 glass vial as a colorless-to-slightly-yellow, sterile, preservative-free clear liquid solution intended for IV administration. The vial is designed to deliver 1.2 mL (150

mg) of atezolizumab solution but may contain more than the stated volume to enable delivery of the entire 1.2 mL volume. The atezolizumab drug product is formulated as 125 mg/mL atezolizumab in 20 mM histidine acetate, 240 mM sucrose, 0.02% polysorbate 20, pH 5.5 (Phase I formulation).

- (2) The atezolizumab drug product produced using the Phase III manufacturing process is provided in a single-use, 20-cc USP/Ph. Eur. Type 1 glass vial as a colorless-to-slightly-yellow, sterile, preservative-free clear liquid solution intended for IV administration. The vial is designed to deliver 20 mL (1200 mg) of atezolizumab solution but may contain more than the stated volume to enable delivery of the entire 20 mL volume. The atezolizumab drug product is formulated as 60 mg/mL atezolizumab in 20 mM histidine acetate, 120 mM sucrose, 0.04% polysorbate 20, pH 5.8 (Phase III formulation).

8.2.5 Storage and Stability

Atezolizumab must be refrigerated at 2°C–8°C (36°F–46°F) upon receipt until use. Atezolizumab vials should not be used beyond the expiration date provided by the manufacturer. No preservative is used in atezolizumab drug product; therefore, the vial is intended for single use only. Discard any unused portion of drug left in a vial. Vial contents should not be frozen or shaken and should be protected from direct sunlight.

8.2.6 Administration

Atezolizumab will be given intravenously at a dose of 1200 mg.

9.0 CORRELATIVE STUDIES

9.1 Peripheral Blood

Patients will have up to 40 mL of blood collected in 4 pink top EDTA tubes at baseline and Cycle 2 Day 1. Patients with hemoglobin below 10 mg/dL will only have 30 mL. 3 EDTA tubes collected.

9.2 Biopsy Samples

When available, archival biopsy tissue will be used for a baseline biopsy. If baseline tissue is not available, the patient will undergo a baseline biopsy prior to initiation of the trial.

When feasible, a repeated tumor biopsy will be obtained between Cycles 2 and 3 after the scheduled CT scan.

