of CD8+ T-cells in the periphery of patients ³⁶⁻³⁸, but despite this, the majority of patients will not derive meaningful benefit from this class of agents, and responses are often not durable. Blunting tumor angiogenesis in order to remodel the tumor microenvironment is an attractive combinatorial approach to synergize with standard immunoncology agents ³⁹. Increased VEGF expression is known to suppress the maturation of antigen-presenting dendritic cells and inhibit lymphocyte tracking into tumor tissues, which can limit the effectiveness of an antitumor adaptive immune response ⁴⁰. We hypothesize that the addition of ramucirumab will augment the clinical activity of atezolizumab, and in order to evaluate the exact mechanism of action of the combination, we propose a comprehensive analysis of paired peripheral blood samples collected longitudinally during this study. We will evaluate whether the combination of atezolizumab and ramucirumab (a) alters populations of circulating monocytes and myeloid derived suppressor cells, (b) increases the number and affects the phenotype of circulating NK cells, effector CD8+ and effector CD4+ T-cell subsets, (c) results in the generation of durable populations of memory CD8+ and CD4+ T-cells and (d) alters the ratio of circulating regulatory T-cells to effector CD8+ cells. We will utilize mass cytometry (CyTOF) for these analyses, a high dimensional technique that allows the assessment of ~40 individual markers using metal labeled antibodies to enable deep profiling of selected phenotypic and functional markers on individual cells as well as unique statistical analyses to simplify the interpretation of complex relationships of large numbers of cells ⁴¹⁻⁴³. We will collect and cryopreserve peripheral blood mononuclear cells prior to combination atezolizumab/ramucirumab therapy and again at the time of first radiographic assessment. Analyses will be completed in a batched fashion using an established mass cytometry panel at the The Andrew M. and Jane M. Bursky Center for Human Immunology & Immunotherapy Programs (CHiPs) at Washington University School of Medicine at the conclusion of study procedures to correlate immune profiles with clinical response. Patients will also undergo repeated biopsy to evaluate the differences in immune cell infiltrates between baseline and after two cycles of treatment.

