3.0 PATIENT SELECTION

3.1 Inclusion Criteria

1. Histologically or cytologically confirmed squamous or non-squamous non-small cell lung cancer. Patients with known EGFR or ALK mutations are eligible only if they have received at least one line of targeted therapy for these mutations.

2. Availability of archival biopsy tissue or willingness to undergo a “baseline” biopsy prior to initiation of the trial for biomarker analysis, including PD-L1 by IHC.

Note: Results of PD-L1 testing are not required for enrollment.

3. Measurable disease defined as lesions that can be accurately measured in at least one dimension (longest diameter to be recorded) as ≥ 10 mm with CT scan, as ≥ 20 mm by chest x-ray, or ≥ 10 mm with calipers by clinical exam.
4. Prior use of an immune checkpoint blocker alone or in combination therapy.
5. At least 18 years of age.
6. ECOG performance status ≤ 1 (see Appendix A)
7. Normal bone marrow and organ function as defined below:
 - a. Absolute neutrophil count $\geq 1,500$ /cumm
 - b. Platelets $\geq 100,000$ /cumm
 - c. Hemoglobin ≥ 9.0 g/dL
 - d. Total bilirubin ≤ 1.5 x ULN
 - e. AST(SGOT)/ALT(SGPT) ≤ 3.0 x ULN or 5.0 x ULN in the setting of liver metastasis
 - f. Serum creatinine ≤ 1.5 x ULN or CrCl ≥ 40 mL/min. if serum creatinine is >1.5 times the ULN, a 24-hour urine collection to calculate creatinine clearance must be performed
8. Adequate coagulation function as defined by:
 - a. INR ≤ 1.5
 - b. PTT/aPTT < 1.5 x ULN

Note: Patients on full-dose anticoagulation must be on a stable dose (minimum duration 14 days) of oral anticoagulant or low molecular weight heparin (LMWH). If receiving warfarin, the patient must have an INR ≤ 3.0 . For heparin and LMWH there should be no active bleeding (that is, no bleeding within 14 days prior to first dose of protocol therapy) or pathological condition present that carries a high risk of bleeding (for example, tumor involving major vessels or known varices).

9. Urinary protein $\leq 1+$ on dipstick or routine urinalysis; if urine dipstick or routine analysis is $\geq 2+$, a 24-hour urine collection for protein must demonstrate < 1 g of protein in 24 hours to allow participation

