10.0 STUDY CALENDAR

Screening/baseline evaluations are to be conducted within 2 weeks prior to start of protocol therapy. Scans and x-rays must be done no more than 4 weeks prior to the start of the protocol therapy. Cycles are 21 days long. There is a +/- 3 day window for all assessments and procedures.

	Screening	Baseline	C1 D1	C2 D1	After Cycle 2	D1 of subsequent cycles	End of every 2 cycles	EOT	F/U ³
Informed consent	X								
H&P, ECOG PS	X			X		X		X	
CBC	X		X	X		X			
CMP	X		X	X		X			
PTT/aPTT, INR	X								
TSH ⁶	X		X						
Hepatitis B and C test	X								
Pregnancy test ¹	X								
Urinalysis	X		X	X		X			
CT scan	X						X		
Ramucirumab			X	X		X			
Atezolizumab			X	X		X			
Research blood		X		X					
Archival tumor		X ⁵							
Fresh biopsy		X ⁵			X ⁴				
Survival									X
AE assessment		X	-----						X ²

1. For women of childbearing potential only

2. For 30 days after end of treatment

3. Every 3 months for 2 years; may be done by phone.

4. When feasible, the biopsy will follow CT scan performed between Cycles 2 and 3

5. When available, archival biopsy tissue will be used for a baseline biopsy. If baseline tissue is not available, the patient will undergo a baseline biopsy prior to initiation of the trial.

6. Reflex to free T3, free T4.

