14.3 Data Analysis

Demographic and clinical characteristics of the sample, as well as toxicity by grade and loss to follow up will be summarized using descriptive statistics. Overall response rate (ORR) and clinical benefit rate (CBR) will be evaluated using the RECIST 1.1 criteria according to investigator's assessment, and their 1-side 90% confidence intervals will also be calculated. Kaplan-Meier product limit estimator will be used to describe the distribution of overall survival (OS) and progression free survival (PFS). The association between response and the immunophenotype of peripheral blood immune cells will be summarized using descriptive statistics. Although data analysis will be primarily descriptive, permutation test will be used to rank the strength of association. Specifically, we first compute the observed test statistics for the differences between responders and non-responders. Then the null distribution of the test statistics will be generated by simulating 10,000 datasets where the status of response was randomly shuffled. The permutation p-values equal the proportion of simulations from the null distribution that exceed the observed test statistics. Similar analysis will be performed for the association between response and the changes in tumor immune cell infiltrate after treatment.

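### Archival tissue of any age takes priority as the tumor baseline, so the change in immune infiltrate can include shifts that occurred before study treatment

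*Combined protocol and SAP*

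**What the plan says.** Section 9.2 sets the order of preference for baseline tissue: "When available, archival biopsy tissue will be used for a baseline biopsy". The alternative applies only in its absence: "If baseline tissue is not available, the patient will undergo a baseline biopsy prior to initiation of the trial". Footnote 5 of the study calendar (Section 10.0) repeats both rules.

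Eligibility does not limit the age of the tissue. Inclusion criterion 2 in Section 3.1 reads: "Availability of archival biopsy tissue or willingness to undergo a “baseline” biopsy prior to initiation of the trial for biomarker analysis, including PD-L1 by IHC". Criterion 4 makes earlier ICB treatment universal: "Prior use of an immune checkpoint blocker alone or in combination therapy". Under criterion 1, patients with known EGFR or ALK mutations are "eligible only if they have received at least one line of targeted therapy for these mutations", so some will have had further treatment lines.

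The second sample is taken, when feasible, between Cycles 2 and 3 after the CT scan (Section 9.2). Section 1.5 gives the purpose: "Patients will also undergo repeated biopsy to evaluate the differences in immune cell infiltrates between baseline and after two cycles of treatment". Exploratory objective 2 (Section 2.3) concerns the infiltrate change after treatment and how it relates to response. Section 14.3 extends the responder versus non-responder permutation analysis to the "association between response and the changes in tumor immune cell infiltrate after treatment".

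**The concern.** A paired-tissue analysis measures the effect of a treatment period only if the first sample reflects the tumor as it was when that period began. Here the first sample may be a diagnostic specimen, taken before the earlier ICB and before any chemotherapy or targeted therapy. Whatever those treatments, or the disease itself, did to the infiltrate in the meantime would be counted in the measured change.

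The protocol's own background makes it unsafe to assume that nothing changed. Section 1.5 describes effects of PD-1-directed therapy on CD8+ T-cells in peripheral blood, and Section 1.4 links failure of ICBs to lower tumor infiltration. The study's mechanistic hypothesis is that VEGFR-2 inhibition brings T-cells into the tumor. The paired biopsies are its only direct look at that in tissue, and a baseline from before the ICB could hide such an increase or imitate one. With a single arm, no control group can remove the pre-study component.

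**Working it through.** The plan states no figure for this analysis, so there is none to reproduce. The check has four parts.

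**1. Does any other rule restrict the tissue date?** Section 10.0 says: "Screening/baseline evaluations are to be conducted within 2 weeks prior to start of protocol therapy". That governs evaluations carried out at screening or baseline and cannot govern when stored tissue was collected. The four-week limit in Section 12.3 belongs to the methods for measuring disease. Section 11.0 schedules a Research Tissue Form at baseline and after Cycle 2 but does not list its fields. Section 14.3 does not adjust for, or stratify by, tissue source, tissue date or intervening therapy. So no rule restricts it.

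**2. Overall change.** Let A be the infiltrate in the archival sample, B the infiltrate just before study treatment, and C the infiltrate after Cycle 2. Then

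C − A = (C − B) + (B − A).

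Only C − B belongs to the study period. If a share q of pairs has early baseline tissue and the mean pre-study shift in those pairs is s = mean(B − A), the mean change is biased by q × s. Neither q nor s is in the documents. With assumed values, in SD of the infiltrate measure:

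| q | s = −0.5 | s = 0 | s = +0.5 | s = +1.0 |
|---|---|---|---|---|
| 0 | 0 | 0 | 0 | 0 |
| 0.25 | −0.125 | 0 | 0.125 | 0.25 |
| 0.5 | −0.25 | 0 | 0.25 | 0.5 |
| 1 | −0.5 | 0 | 0.5 | 1.0 |

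The bias vanishes if q = 0 or s = 0. The plan secures neither.

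**3. Responder contrast, the comparison that Section 14.3 specifies.** With subscripts R and N for responders and non-responders, the bias is q_R × s_R − q_N × s_N.
- Same share and same shift in both groups (q = 0.5, s = 0.5): 0.25 − 0.25 = 0.
- Different shares (q_R = 0.25, q_N = 0.75, s = 0.5 in both): 0.125 − 0.375 = −0.25 SD.

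The table in part 2 therefore does not carry over to this contrast, which is biased only when share or shift differs by response.

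**4. What would restricting the analysis to late baselines cost?** Suppose 50% to 80% of baselines are early (again an assumption). Of 21 patients, 21 × 0.2 = 4.2 to 21 × 0.5 = 10.5 pairs remain, or about 4 to 10, even if every repeat biopsy is obtained. Section 1.6.1 reports no responses in the first 12 patients. If none of them responds later and the remaining 9 respond at the 20% target rate, 9 × 0.20 = 1.8 responders are expected. The restricted set would then hold 1.8 × 0.2 = 0.36 to 1.8 × 0.5 = 0.9 of them. A responder comparison confined to late baselines would probably be impossible.

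**The case against.** The strongest reply is that the plan claims little. Section 14.3 calls the analysis mainly descriptive and uses permutation tests to rank associations. Section 1.5 ties its language on mechanism of action to the paired blood samples, which have a study baseline draw. No decision depends on the tissue result, and a caveat in the report might be enough.

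Much of this stands. A reader might infer that the plan formally attributes the whole archival-to-post-Cycle-2 difference to ramucirumab plus atezolizumab. It does not; it speaks of differences and of change after treatment. A reader might also infer that the answer is biased by a known amount. The documents give no share of early samples and no shift, and an illustration for the mean change does not describe the responder contrast. Nor do they show that tissue and ICB dates are already captured: the forms are named, but their fields are not.

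Another tempting step is to base the main analysis only on tissue taken after the last ICB dose. That would lose most of an already small set, as shown above, and would still admit tissue followed by a later non-ICB treatment.

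What the reply does not answer is that a result labelled as change after treatment can contain change from before treatment, and that the plan neither records nor uses what is needed to tell the two apart. A caveat written afterwards cannot separate the pairs if the dates were not collected.

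**Conclusion.** The point holds as a limited one. As written, the plan allows the infiltrate change to include shifts from before Cycle 1 Day 1. Confounding of the overall change requires that some archival samples predate intervening therapy and that the infiltrate shifted in between. Confounding of the responder contrast also requires that the share or the shift differ by response. Size and direction cannot be derived from the documents; every SD figure above rests on assumed inputs.

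The consequence is confined to exploratory objective 2. Response rate, survival endpoints, clinical benefit rate, toxicity and the blood correlatives are unaffected.

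**What to change.** 1. On the Research Tissue Form, record the collection date of the baseline tissue relative to the last ICB dose, and any therapy given between collection and Cycle 1 Day 1.
2. In Section 14.3, pre-specify that the change is reported separately for (a) pairs whose baseline was taken after the last prior systemic therapy and (b) pairs with earlier baseline tissue. State that only (a) is interpreted as change over study treatment.
3. Keep all pairs in the responder permutation analysis. Shuffle response status within (a) and (b) where numbers allow, and add a sensitivity analysis in (a). A group in which all patients have the same response status adds no information to the stratified shuffle; the report should say so if this happens.

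The cost is a few data items, which may have to be retrieved from source records for patients already enrolled, and a short addition to Section 14.3. The subgroups will be small and group (a) may be very small. No pairs are discarded and no biopsy is added.
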